4.1 Population

According to the latest epidemiological survey of stroke in China in 2020, the standardized prevalence of stroke in China is 2.6%, with an incidence rate of 505.2 per 100,000 person-years and a mortality rate of 343.4 per 100,000 person-years^[23]. Among individuals aged 40 years and older, there are approximately 17.8 million prevalent stroke cases, 3.4 million new cases, and 2.3 million stroke-related deaths annually^[23]. From 1990 to 2019, while the incidence and mortality rates of stroke have shown a gradual decline in Western countries, the overall burden of stroke in China has significantly increased^[24]. During this period, the prevalence of stroke in China grew by 106%, reflecting that stroke has become a major public health challenge in the country.

4.2 Participating center and center qualification

A eligible participating center must meet the following minimum qualifications:

- (1) Tertiary hospital in their respective region.
- (2) Previous experience as a leader or participant in AIS clinical trials.
- (3) Capability to perform both IVT and EVT, with at least 30 AIS cases with EVT conducted annually.
- (4) Median door-to-needle time (DNT) < 60 minutes and door-to-puncture time (DTP) < 90 minutes.

* The previous experience indicates that the interventional team has the experience in endovascular procedures for cerebrovascular diseases (e.g., EVT, vertebral artery or basilar artery stenting, aneurysm coiling), peripheral arterial diseases, or coronary arterial diseases. The stroke team (including neurologists and interventionalists should have expertise in intra-arterial treatment. The intervention team is proficient in using one or more devices approved by the National Medical Products Administration (NMPA). At least one team member has the experience of using specific interventional devices.

Note: A patient can only be enrolled in the trial after being evaluated by an intervention team which must include at least one intervention specialist with EVT experience.

4.3 Inclusion criteria

Participants must meet all of the following criteria to be eligible for enrollment:

- (1) A clinical diagnosis of AIS.

(2) Caused by BAO confirmed by CTA, MRA, or DSA. (BAO is defined as the absence of visualization of the basilar artery on CTA, MRA or DSA. Bilateral vertebral artery occlusions or occlusion of a unilateral vertebral artery that is the sole supplier of the basilar artery, even in the presence of patent basilar artery, will be considered de facto BAO.)

(3) CT or MRI ruling out intracranial hemorrhage,

(4) Eligible for IVT and EVT (within 4.5 hours of symptom onset). (Symptoms onset is defined as point in time the patient was last seen well [at baseline] if patients are unable to provide a reliable history or the point in time when symptoms have started if patients can provide a reliable history. Symptoms onset includes diplopia, midline ataxia, visual loss, sensory or motor deficits, and conscious disturbance. Isolated vertigo [not accompanied by dysarthria, motor weakness, sensory symptoms, double vision, depressed level of consciousness] is not considered onset of symptoms.)

(5) NIHSS score ≥ 6 .

(6) Age ≥ 18 years.

(7) Signed informed consent by the patient or legal representative.

4.4 Exclusion criteria

Potential participants will be excluded from the study if they meet any of the following criteria:

(1) mRS score > 2 before this stroke.

(2) Any contraindication to IVT as per the 2019 AHA/ASA guidelines for early management of AIS:

1) Blood pressure $> 185/110$ mmHg and cannot be controlled by standard medication,

2) Blood glucose < 50 mg/dL (2.8 mmol/L) or > 400 mg/dL (22.2 mmol/L),

3) Had a cerebral infarction in the previous 6 weeks with residual neurological deficit or signs of recent infarction on neuroimaging,

4) Severe head trauma in the previous 3 months,

5) Major surgery or severe trauma in the previous 2 weeks,

6) Gastrointestinal or urinary bleeding in the previous 3 weeks,

7) previous intracranial hemorrhage,

8) Using anticoagulants and International normalized ratio (INR) > 1.7 ,

9) Known platelet count $< 100 \times 10^9/L$,

10) treatment with direct thrombin or factor X inhibitors,

11) Heparin treatment in the previous 48 hours with the activated partial thromboplastin time (APTT) exceeding the upper limit of normal.

(3) Pregnancy, breastfeeding, or intention to conceive during the study period.

(4) Other conditions deemed unsuitable by the investigator.

4.5 Sample size

Currently, no large-scale RCTs exist in this field. The sample size calculation for this study is based on the findings of the RESCUE-RE registry study conducted in the Chinese population^[25]. According to the study, the proportion of patients achieving a mRS score ≤ 2 at 90 \pm 14 days post-procedure was 42.03% in the IVT followed by EVT group and 26.14% in the EVT alone group. Based on a superiority hypothesis, this study aims to determine whether the good outcome rate (90-day mRS ≤ 2) in the IVT followed by EVT group is superior to that of the EVT alone group. Assuming a one-sided type I error rate of 0.025 and 80% statistical power, and using a 1:1 randomization ratio, a total of 272 patients (136 per group) is required. Accounting for an anticipated dropout rate of approximately 20%, the final sample size is adjusted to 340 patients, with 170 patients per group.

This study hypothesizes that IVT followed by EVT is superior to EVT alone. However, given the limited

reference data and clinical evidence in the anterior circulation indicating that EVT alone may be non-inferior to IVT followed by EVT, an interim analysis is planned after one-third (114) of patients complete follow-up for the primary endpoint. During this interim analysis, the Data and Safety Monitoring Board (DSMB) will evaluate the efficacy data from both groups and conduct a sample size re-estimation based on the calculated conditional power. Based on the available data, the DSMB will provide recommendations to the BEST-BAO research team on whether to adjust the sample size or modify the study hypothesis.

If the efficacy advantage of the IVT followed by EVT group over the EVT alone group is less than anticipated, the sample size may be expanded appropriately, with an upper limit of no more than 20% of the original sample size. If the efficacy of the two groups appears to be similar, the study design will shift to a non-inferiority framework, evaluating whether EVT alone is non-inferior to IVT followed by EVT. Assuming similar efficacy (with both groups achieving a 90-day mRS score ≤ 2 in 42.03% of patients), the current sample size of 170 patients per group provides 80% power to test non-inferiority, with a one-sided type I error rate of 0.025 and a non-inferiority margin of -15% in rate difference. The interim analysis and sample size re-estimation will be conducted under the strict control of the DSMB to ensure that the type I error rate is not inflated.

5. Intervention

5.1 Study treatment

Patients in the IVT followed by EVT group will receive IVT with rtPA (0.9 mg/kg, maximum 90 mg in one hour), which is followed by EVT. Patients in the EVT alone group will not receive IVT and will undergo EVT alone.

Note: The efforts should be made to minimize delays in EVT initiation caused by IVT procedure in the IVT followed by EVT group. For patients undergoing screening evaluation by CTA or MRA, the time from randomization to femoral artery puncture should be as short as possible, with all patients aiming to achieve a median time of 60 minutes or less from randomization to groin puncture and prompt completion of the guiding catheter inserting into the vascular puncture sheath. For patients undergoing screening evaluation by DSA, the guiding catheter insertion into the vascular puncture sheath should be completed as quickly as possible after randomization according to the assigned treatment strategy. We will record and compare the time from onset to door, from onset to screening imaging, from last non-invasive imaging to groin puncture in the DSA randomized patients, from onset to randomization, from hospital admission to IVT, from hospital admission to groin puncture, from hospital admission to guiding catheter inserted into vascular puncture sheath, from randomization to IVT, from randomization to groin puncture, from randomization to guiding catheter inserted into vascular puncture sheath, and from randomization to cerebrovascular reperfusion/recanalization between the two groups

In this trial, the initiation time of EVT procedure is defined as the moment the guiding catheter is inserted into the vascular puncture sheath in preparation for subsequent therapeutic procedures which may include retrievable stent thrombectomy, thrombus aspiration, balloon angioplasty, stent implantation, or combinations thereof. The end time of EVT procedure is defined as the moment all devices in the vascular puncture sheath are removed (regardless of whether the vascular puncture sheath is retained for a short period of time). The specific EVT approach for each patient will be determined by the treatment team based on the individual's clinical condition. Vascular imaging processes conducted before EVT initiation, including CTA, MRA, and DSA, are all considered vascular screening procedures during the screening phase.

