8.2 Randomization, blinding, and treatment allocation

The randomization process will use a web-based randomization system. Patients can be randomized (**Appendix 16**) when AIS-BAO is confirmed by CTA, MRA, or DSA.

Before a patient is registered in the study database, assigned groups and treatment allocation will remain inaccessible, and patients cannot be excluded from the study after the allocation is revealed. Both patients and treating physicians will be aware of the assigned treatment group. However, trained investigators, who are blinded to assigned groups and treatment allocation, will record endpoint-related information using standardized forms and procedures, and details of the interviews. These trained evaluators will assess mRS outcomes and evaluate neuroimaging results in a blinded manner. Information related to assigned groups and treatment allocation will be maintained separately from the study database. The SC will not be informed of interim analysis results on the efficacy and safety. Independent trial statisticians will combine treatment allocation data with study database for reporting to the DSMB.

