Appendix 19. Steering committee recommendations on IVT and EVT procedures

1. Basic recommendations

All eligible patients should undergo trial enrollment, randomization, and subsequent EVT (with or without prior IVT) as quickly as possible after arrival.

The efforts should be made to minimize delays in EVT initiation caused by IVT procedure in the IVT followed by EVT group. For patients undergoing screening evaluation by CTA or MRA, the time from randomization to femoral artery puncture should be as short as possible, with all patients aiming to achieve a median time of 60 minutes or less from randomization to groin puncture and prompt completion of the guiding catheter inserting into the vascular puncture sheath. For patients undergoing screening evaluation by DSA, the guiding catheter insertion into the vascular puncture sheath should be completed as quickly as possible after randomization according to the assigned treatment strategy. We will record and compare the time from randomization to femoral artery puncture, to the guide catheter insertion into the vascular puncture sheath, and to cerebrovascular reperfusion or recanalization between the two groups.

In this trial, the initiation time of EVT procedure is defined as the moment the guiding catheter is inserted into the vascular puncture sheath in preparation for subsequent therapeutic procedures which may include retrievable stent thrombectomy, thrombus aspiration, balloon angioplasty, stent implantation, or combinations thereof. The end time of EVT procedure is defined as the moment all devices in the vascular puncture sheath are removed (regardless of whether the vascular puncture sheath is retained for a short period of time). The specific EVT approach for each patient will be determined by the treatment team based on the individual's clinical condition. Vascular imaging processes conducted before EVT initiation, including CTA, MRA, and DSA, are all considered vascular screening procedures during the screening phase.

We will document the actual dose, type, route, and administration time of IVT medications. Additionally, we will record the time intervals from symptom onset to emergency department arrival, CT/MR/DSA imaging, randomization, IVT initiation, EVT procedure initiation, reperfusion, and EVT procedure completion.

2. Neuroimaging

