Appendix 20. Imaging requirements

Baseline Imaging minimum requirements

When

Prior to randomization, a CT/CTA, MRI/MRA, or CT/DSA should be performed to assess eligibility criteria.

How

1. Pre-randomization CT:

(1) Positioning and scope: The patient should lie in a supine position, with both sides of the head symmetrically aligned. The external auditory meatus on both sides should be equidistant from the table, and the chin should be slightly tucked. Scanning should cover a continuous range of 100–120 mm from the baseline upwards.

(2) Scan reference line: Use the standard orbitomeatal line (a line between the outer canthus of the eye and the external auditory canal). This line roughly parallels the skull base, minimizing bone artifacts and improving visualization of posterior fossa structures.

(3) Tube voltage: 120 kV.

(4) Tube current: 200–300 mA.

(5) Slice thickness and interval: Standard slice thickness of 5–8 mm, with an interval of 5–8 mm.

(6) Window width and window level: Brain window: level = 30–40 HU, width = 70–100 HU. Bone window: level = 250–500 HU, width = 1000–1600 HU. Bone windows typically use a bone algorithm.

2. Pre-randomization CTA:

(1) CTA coverage: It is recommended that the CTA cover the entire region from the aortic arch to the top of the head.

(2) Procedure: Contrast agent: Use a non-ionic, iso-osmolar iodine contrast agent with a concentration of 300 mgI/dL, with a total volume of 90 ml. Injector settings: Set the flow rate at 4 ml/second for the first 30 ml, followed by 3 ml/second for the remaining 60 ml. Scanning: Start the CTA scan simultaneously with the high-pressure injector, guided by Bolus tracking software to ensure optimal timing. The scan range should extend from the aortic arch to the cranial vertex. Use a tube voltage of 120 kV, tube current of 150 mA, slice thickness of 0.5–1.5 mm, and set the reconstruction interval to half of the slice thickness.

(3) Image processing: Image Processing: Provide at least one Maximum Intensity Projection (MIP) image from the CTA data set to assess vascular parameters. Generate three-dimensional volume rendering (VR) and three-dimensional MIP images for vascular visualization. Pay special attention to the original CTA data, particularly the bilateral subclavian arteries and vertebral arteries.

(4) CTA original images: Reconstruct the original CTA images with a slice thickness of 10–12 mm to evaluate the presence of acute infarct lesion.

3. Pre-randomization MRI/MRA:

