(1) Scan baseline: Parallel to the anterior-posterior commissure line.

(2) Routine MRI Sequences: Axial SE T1WI: Slice thickness 5–8 mm; interslice gap 1–2.5 mm; 15–25 slices; matrix: 256 × 192–512 × 256; field of view (FOV): 220–250 mm. Axial FSE T2WI: Same specifications as above. Sagittal SE T1WI or FSE T2WI: Helps display midline structures.

Coronal SE T1WI or FSE T2WI: Useful for showing lesions near the skull base or vertex.

(3) FLAIR sequence: Axial plane: TR 10000 ms; TE 100 ms; inversion time (TI) 2000 ms; FOV 230 mm × 230 mm; matrix: 128 × 128; slice thickness: 6 mm; interslice gap: 1.8 mm.

(4) DWI sequence: Axial plane, EPI sequence with b-values of 0 and 1000 s/mm²; TR 3100 ms; TE 99 ms; FOV 230 mm × 230 mm; matrix: 128 × 128; slice thickness: 6 mm; interslice gap: 1.8 mm.

(5) MRA (TOF): TR 22 ms; TE 3.86 ms; FOV 230 mm × 230 mm; slice thickness 0.65 mm; interslice gap: -0.15 mm; 48 slices; flip angle: 18°; number of acquisitions: 1. Scanning range from the C1 lower border to the lateral ventricles' upper border.

4. Pre-randomization DSA:

- (1) Baseline DSA should avoid guide catheter use to save time for IVT or EVT initiation.
- (2) Intracranial artery baseline and final anteroposterior (AP) and lateral views are mandatory.
- (3) Baseline DSA must include arterial and venous phases to assess the cause of BAO.
- (4) Baseline DSA should assess proximal vessels supplying the basilar artery (subclavian artery, vertebral artery, and anterior/posterior collateral circulations).

Post-acquisition requirements:

1. All imaging (CT/CTA, MRI/MRA, and CT/DSA) must be stored in DICOM format.
2. All imaging data, including CT, CTA, MRA, and DSA, should be interpreted by at least two neurointerventional or radiology specialists at each participating center. These specialists will not be directly involved in the execution of the trial.
3. All imaging series must be submitted to the independent imaging adjudication committee for further evaluation.

Angiography During EVT

When

1. During EVT procedure, perform anteroposterior and lateral angiographic views (covering the entire head, including the venous phase) to evaluate the occlusion site, clot burden, affected area, associated pathologies, and collateral circulation.
2. Perform angiography after each passage of mechanical or aspiration devices.
3. Perform angiography after each bolus injection of thrombolytic agents.

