### 3.9.3 Subgroup analysis

Subgroup analysis of the primary efficacy endpoint will be conducted based on the following factors (m-ITT set):

- (1) Age
- (2) Sex
- (3) Medication history
- (4) Pre-stroke mRS score
- (5) Baseline stroke severity (NIHSS score)
- (6) Blood glucose level at admission
- (7) Baseline infarct size (PC-ASPECTS score and quantitative measurement)
- (8) Baseline collateral circulation status (PC-CS and BATMAN scores)
- (9) Stroke etiology
- (10) Location of basilar artery occlusion
- (11) Time from symptom onset to randomization

- (12) Time from randomization to groin puncture
- (13) Time from randomization to guiding catheter insertion into the vascular puncture sheath
- (14) Time from randomization to cerebrovascular reperfusion

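### Randomisation-to-groin-puncture time is compared between arms without regard to screening route, although in DSA-screened patients the puncture normally precedes randomisation; this dilutes the interval and mixes screening route into subgroup item 12

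*Protocol*

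**What the plan says.** **When patients are randomised.** Protocol 8.2 allows randomisation "when AIS-BAO is confirmed by CTA, MRA, or DSA". Appendix 20 puts that imaging first: "Prior to randomization, a CT/CTA, MRI/MRA, or CT/DSA should be performed to assess eligibility criteria". Section 5.1 classes DSA as screening: "Vascular imaging processes conducted before EVT initiation, including CTA, MRA, and DSA, are all considered vascular screening procedures during the screening phase".

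**What is compared.** Section 5.1 lists the intervals to be recorded and compared between the groups, including "from randomization to IVT, from randomization to groin puncture, from randomization to guiding catheter inserted into vascular puncture sheath", and ends with randomisation to reperfusion or recanalisation. Appendix 19 repeats a shorter list: "We will record and compare the time from randomization to femoral artery puncture, to the guide catheter insertion into the vascular puncture sheath". Neither list limits the puncture interval to a screening route. In the SAP the interval appears only as a subgroup factor for the primary endpoint, "Time from randomization to groin puncture" (3.9.3, item 12, m-ITT set). Protocol 10.3 has the same item.

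**Where the plan does separate the routes.** Section 5.1 gives CTA/MRA-screened patients a timing goal on puncture, and DSA-screened patients a goal on guiding-catheter insertion. It also has an interval from the last non-invasive imaging to puncture that applies only to patients randomised after DSA. It defines the start of EVT as guiding-catheter insertion, not puncture. On the screening angiogram, Appendix 20 says: "Baseline DSA should avoid guide catheter use to save time for IVT or EVT initiation".

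**The concern.** DSA needs arterial access. A patient randomised after screening DSA will normally have been punctured already, so the time from randomisation to puncture is negative and was fixed before allocation. Nothing in the assigned strategy can alter it. The authors evidently saw this when they set the timing goals and added the DSA-only interval, but they did not carry it into the between-arm comparison or the subgroup list.

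Two things are at stake. The protocol asks that IVT should delay EVT as little as possible, and this interval is one of the checks. Pooling in patients whose value cannot respond weakens that check, so an unremarkable puncture comparison could be reported beside a real delay. In subgroup item 12, the DSA-screened patients hold the lowest values by construction, so a contrast of short against long times becomes in part a contrast of screening routes.

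**Working it through.** The documents give no DSA share, no expected interval and no expected IVT delay, so there is no plan figure to reproduce. All timing inputs below are assumptions. Only the 170 per arm comes from the documents (Protocol 4.5).

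**1. Mean difference.** Let *f* be the DSA share and *d* the delay that IVT causes in CTA/MRA-screened patients. DSA-screened patients contribute zero difference, so the pooled mean difference is (1 − *f*) × *d*. With *d* = 7 minutes:
- *f* = 10%: 0.9 × 7 = 6.3 min
- *f* = 20%: 0.8 × 7 = 5.6 min
- *f* = 30%: 0.7 × 7 = 4.9 min
- *f* = 50%: 0.5 × 7 = 3.5 min

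**2. Rank-test power.** Simulation of 1,500 trials per setting, two-sided 0.05. Assumed times: puncture 40 min (SD 20) after randomisation in CTA/MRA-screened patients and 25 min (SD 10) before it in DSA-screened patients; delay 7 min.

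| DSA share | Power, all patients pooled | Power, CTA/MRA only |
|---|---|---|
| 10% | 71% | 84% |
| 20% | 52% | 81% |
| 30% | 33% | 75% |
| 50% | 12% | 62% |

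Hand check of the 20% row, CTA/MRA only: 0.8 × 170 = 136 per arm; standard error 20 × √(2/136) = 2.43; 7/2.43 = 2.89; 2.89 − 1.96 = 0.93, which corresponds to about 82%. This agrees with the simulated 81%. The restricted analysis has fewer patients but more power in every row.

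**3. Medians.** On the same assumptions the pooled difference in medians averages 7.0, 7.0, 7.2 and 6.8 min at shares of 10, 20, 30 and 40%, and about 3 min at 50%. The reason is that the pooled median reads the (0.5 − *f*)/(1 − *f*) quantile of the CTA/MRA-screened patients: the 37.5th percentile at 20% (0.3/0.8) and the 28.6th at 30% (0.2/0.7). A constant delay shifts every quantile equally. At 50% the median falls in the gap between the two clusters.

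**4. Other assumptions, and the guiding-catheter interval.** With a 10-minute delay and lognormal times (medians 40 min to puncture for CTA/MRA, 15 min from puncture to randomisation for DSA, 10 min to the guiding catheter), puncture power falls from 0.997 with no DSA patients to 0.84 at 20%, 0.60 at 30% and 0.21 at 50%. For randomisation to guiding catheter, the mean difference stays at about 10 min and power between 0.93 and 0.997 at every share.

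**5. Subgroup item 12.** The plan gives no cut-points; a split into thirds is assumed. If all DSA-screened patients fall in the shortest third, their share of it is *f* ÷ (1/3): 0.20 × 3 = 60% and 0.30 × 3 = 90%. Simulation gives about 60% and 89%.

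**The case against.** **The delay is measured elsewhere.** A reader might infer that the plan hides any delay that IVT causes to EVT. The documents do not support that. The same sentence in 5.1 also compares randomisation to guiding-catheter insertion, which is the protocol's own start of EVT, and randomisation to reperfusion. SAP 3.8 describes times from onset by arm, including the start of EVT. A delay would show there, in DSA-screened patients as well. This part of the objection stands in full.

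**The loss depends on the summary.** The puncture target in 5.1 is a median, and SAP 3.2.2 requires medians and quartiles. Up to about a 40% DSA share the median difference keeps nearly the whole delay. This also stands: the harm is to means and rank tests.

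**It is a process measure.** No named test or decision rule is attached to the interval. It is not an endpoint, and SAP 3.8 does not list it. That limits the weight of the point, but 5.1 and Appendix 19 do promise a between-arm comparison.

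**Puncture before randomisation is inferred.** The documents never state it outright, and a different access site for DSA and EVT would be an exception. The inference is nevertheless well supported by the separate timing goals in 5.1.

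**Subgroup 12 has other problems.** The share in the shortest third depends on an unspecified split. Items 12 to 14 are all times running from randomisation that treatment can influence, and restricting item 12 does not cure that.

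**IVT intervals.** A reader might also object that times to IVT are compared between groups although one arm is not assigned IVT. Nothing in the plan says that rescue IVT times would be pooled with assigned IVT, so this is loose list wording rather than an analysis defect.

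**Conclusion.** The point holds in a limited form. As written, the randomisation-to-groin-puncture comparison and subgroup item 12 include patients whose value is normally negative and settled before allocation. The mean arm difference shrinks to (1 − DSA share) of its value. Rank-test power drops from about 81% to 52% at a 20% share, on the assumed 7-minute delay and assumed time distributions. Median differences are nearly intact up to about a 40% share, given a constant delay. Item 12 becomes in part a comparison by screening route, to a degree set by the DSA share and the cut-points, neither of which is given. The other delay measures and the primary endpoint and its test are unaffected.

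**What to change.** - In Protocol 5.1 and Appendix 19, restrict the between-arm comparison of randomisation to groin puncture to patients screened by CTA or MRA.
- Name randomisation to guiding-catheter insertion as the measure of delay for all patients, shown overall and by screening route. Note that Appendix 20 only recommends against a guide catheter at baseline DSA, so any patient in whom one was placed before randomisation should be identified.
- In Protocol 10.3 and SAP 3.9.3, apply the same CTA/MRA restriction to item 12. It remains a subgroup formed after randomisation and should be read with that caution.

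The cost is wording. The times and the screening modality are already recorded (Protocol 5.1 and 8.1.4). The downside is that the puncture comparison and item 12 use fewer patients. For the puncture comparison, the working shows that power rises all the same under the stated assumptions.
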